## **8. STUDY POPULATION**

In general, subjects who signed informed consent and were enrolled for the study will be used for data summaries and listings for subject disposition. Safety population will be used for safety summaries and listings, while the ITT and Evaluable Populations will be used for efficacy analyses, unless otherwise specified.

### **8.1. Subject Disposition**

#### **8.1.1. Subject Enrollment and Disposition**

A summary of subject disposition will be provided and will present the number of subjects enrolled, and the number and percent of subjects:

- Included in the Safety population;
- Included in the ITT population;
- Included in the Evaluable population;
- Completing the study (includes the study treatment period, day 3 in-hospital visit, and at least one of the post-treatment safety follow-up visits); and
- Not completing the study, (with summary of reasons for not completing the study).

[REDACTED]

[REDACTED]

#### **8.1.2. Exposure to Study Drug**

Extent of exposure to study drug will be summarized for the safety population. [REDACTED]

[REDACTED]

### **8.2. Protocol Deviations**

All protocol violations and deviations will be summarized by classification category (major/minor) and provided in a data listing. Subjects with major protocol deviations will be excluded from the Evaluable analysis population. Before database lock a Data Review Committee will document decisions around major/minor protocol deviations.

### **8.3. Inclusion/Exclusion Criteria**

A listing will be provided for screen failures, defined as subjects in the Enrolled population who do not meet all inclusion criteria or who meet at least one exclusion criterion, along with the criterion number and description not met.

### **8.4. Demographics and Baseline Characteristics**

Subject demographic data (e.g., age, sex, race, and ethnicity) and baseline characteristics (e.g., body weight, height, BMI) will be summarized using descriptive statistics (sample size, mean, standard deviation, median, Q1, Q3, minimum and maximum) for continuous data and by the number and percent of subjects for categorical data. The summaries of demographic data and baseline characteristics will be provided for the safety analysis set.

### **8.5. Medical History**

Medical history will be summarized by Medical Dictionary for Regulatory Activities (MedDRA) system organ class (SOC) and preferred term (PT) (using minimum version 26.1). Participants will only be counted once at each level of summation. Summaries will be sorted by decreasing total incidence by SOC (overall) and then by PT (within each SOC); for SOC or PTs (within SOC) with the same frequency, sorting will be performed alphabetically. By-participant listings of this information will also be provided along with onset and resolution dates and grades (collected in the CRF if the condition is ongoing).

### **8.6. Prior and Concomitant Medications**

Concomitant medications are defined as medications that started on or after the treatment start date or were ongoing at the date of treatment start. Prior medications are defined as medications that started and stopped prior to the date of treatment start.

Medications will be coded using the World Health Organization (WHO) Drug Dictionary B3 Global (updated September 2023). Anatomical Therapeutic Chemical (ATC) Level 4 drug classes and preferred drug names (PN) will be attached to the clinical database. The number and percentage of subjects with at least one instance of medication use will be summarized by ATC class and PN (within ATC class) ordered by decreasing total incidence of ATC and PN (within ATC); ties in frequency will be broken alphabetically. Patients will only be counted once at each level of summation. By-participant listings will also be provided.

## **9. EFFICACY ANALYSES**

### **9.1. Definition of the Primary Efficacy Endpoint**

The proportion of subjects with at least one Clinically Significant Event (CSE) as defined by:

1. Intraoperative localization of one or more preoperatively identified lung lesions using VGT-309 with NIR imaging when standard surgical techniques using white light and/or palpation failed to identify the lesion(s), and lesion(s) are confirmed by histologic examination to be other than normal lung tissue.

2. Identification of one or more synchronous or occult lung lesions using VGT-309 with NIR imaging when standard surgical techniques using white light and/or palpation and preoperative imaging failed to identify the lesion(s), and lesion(s) are confirmed by histologic examination to be cancerous or precancerous.
3. Identification of fluorescence within  $\leq 10$  mm from the inside edge of the closest staple line as measured by the investigator *ex vivo* in the operating room using NIR imaging, with pathologic margin confirmed by histologic examination to be  $\leq 10$  mm. NOTE: Margins from excisions of known or suspected metastases at the time of the surgery, OR diagnostic wedge resections where a completion lobectomy or segmentectomy was subsequently performed, will not be considered for Margin CSE inclusion.
4. Identification of lymph nodes by VGT-309 with NIR imaging confirmed by histologic examination to be cancerous.

## 9.2. Statistical Hypothesis for the Primary Efficacy Endpoint

The primary study hypothesis is that VGT-309 with NIR imaging is superior to white light and palpation for the intraoperative localization of preoperatively identified lung lesions. The null hypothesis for the primary endpoint is that  $\leq 10\%$  of subjects will have at least one CSE, while the alternative hypothesis is that proportion of subjects with at least one CSE will exceed 10%.

For the primary endpoint analysis, the proportion of subjects with at least 1 CSE will be tested under the null hypothesis that this proportion is  $\leq 10\%$ .

$$H_0: p \leq 0.10$$

The alternative hypothesis states that the proportion of evaluable subjects with at least 1 CSE will be greater than 10%:

$$H_a: p > 0.10$$

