10.3 Hypothesis Tests

10.3.1 Treatment Comparisons

There is only one treatment in this unblinded single-arm study. The hypothesis to be tested is not a treatment comparison. The hypothesis to be tested is that the lower bound of a 95% confidence interval for the observed proportion of subjects with at least one CSE exceeds 10%.

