10.3.2 Primary Hypothesis

The primary study hypothesis is that VGT-309 with NIR imaging is superior to white light and/or palpation for the intraoperative localization of preoperatively identified lung lesions.

The null hypothesis for the primary endpoint is that $\leq 10\%$ of subjects will have at least one CSE, while the alternative hypothesis is that proportion of subjects with at least one CSE will exceeds 10% as demonstrated by at least 15/86 (17.4%) evaluable subjects with at least one CSE.

For the primary endpoint analysis, the proportion of subjects with at least 1 CSE will be tested under the null hypothesis that this proportion is $\leq 10\%$.

$$H_0: p \leq 10\%$$

The alternative hypothesis states that the proportion of evaluable subjects with at least 1 CSE will be greater than 10%:

$$H_a: p > 10\%$$

The primary analysis will use the EP population. This analysis may be repeated using the ITT population. One-sided 2.5% exact binomial test will be used to test the null hypothesis. Clopper-Pearson exact two-sided 95% confidence intervals will be reported.

For the secondary endpoint analysis sensitivity, PPV, and 1-PPV will be calculated and presented along with 95% confidence intervals using GEE model analysis to factor in within-subject correlation for subjects with multiple tumors.

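### The stated primary hypothesis is superior localization of known lesions, but the test covers any of four event types, so rejecting H0 does not support it

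*SAP*

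**What the plan says.** Protocol 10.3.2 gives the primary study hypothesis as "VGT-309 with NIR imaging is superior to white light and/or palpation for the intraoperative localization of preoperatively identified lung lesions". SAP 9.2 repeats it with a small change of wording: "VGT-309 with NIR imaging is superior to white light and palpation for the intraoperative localization of preoperatively identified lung lesions".

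Both sections then set up a different quantity. In SAP 9.2, "the proportion of subjects with at least 1 CSE will be tested under the null hypothesis" that the proportion is at most 10%, against the alternative that it is larger. Protocol 10.3.2 has the same pair and adds the success threshold of 15/86.

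SAP 9.1 defines the endpoint as "The proportion of subjects with at least one Clinically Significant Event (CSE) as defined by" four event types, any one of which counts. They are numbered 1 to 4 in the SAP and lettered A to D in Protocol 2.2.1:

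- Type 1/A: "Intraoperative localization of one or more preoperatively identified lung lesions using VGT-309 with NIR imaging when standard surgical techniques" have failed to find them.
- Type 2/B: "Identification of one or more synchronous or occult lung lesions using VGT-309 with NIR imaging", where standard techniques and preoperative imaging had both missed them.
- Type 3/C: fluorescence close to the staple line, measured ex vivo, with a close margin confirmed by pathology.
- Type 4/D: lymph nodes identified by NIR and confirmed as cancerous.

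SAP 9.3 specifies a one-sided exact binomial test at 0.025 with a two-sided 95% Clopper-Pearson interval for the composite. By CSE type it plans a frequency summary across subject characteristics.

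**The concern.** The sentence labelled as the primary hypothesis describes one of the four components. Type B is by definition about lesions that were not known before surgery. Types C and D are not about localizing a lung lesion, and neither requires that white light or palpation failed. A trial that meets its threshold through margins and nodes would therefore reject H0 without evidence on the claim that the documents attach to that test.

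No other analysis in the visible text fills the gap. The secondary endpoints compare fluorescence with histology, not with white light or palpation. What is at stake is the conclusion that the trial may draw from a positive result, not its error rate.

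**Working it through.** **Inputs.** From the protocol synopsis (Statistical Methods): null rate 10%, design rate 20%, 86 evaluable subjects, success at 15 or more, interval at 15/86 of 10.1% to 27.1%. From SAP 9.3: exact one-sided test at 0.025. Component rates: none in the documents, so all of those below are assumptions.

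**Step 1: the plan's own figures.**

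- Sample size by normal approximation: ((1.96 × √(0.10 × 0.90) + 0.842 × √(0.20 × 0.80)) / 0.10)² = 85.5, rounded up to 86.
- Type I error of the rule: P(X ≥ 15 | n = 86, p = 0.10) = 0.0230, below 0.025. A threshold of 14 would give 0.0461.
- Clopper-Pearson interval at 15/86: 10.1% to 27.1%, as stated.

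All three reproduce, and all refer to the composite.

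**Step 2: the extreme case, which needs no rate assumption.** Suppose that 15 subjects have a type B, C or D event and none has type A. The composite is 15/86 and H0 is rejected. Type A is 0/86, with upper 95% Clopper-Pearson limit 1 − 0.025^(1/86) = 4.2%. The rule is met with no localization event.

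**Step 3: the probability of success under assumed rates.** With independence, the composite rate is 1 − (1 − pA)(1 − pBCD), where pBCD is the rate of any of B to D. Success is P(X ≥ 15 | 86, composite rate).

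| Type A | Any of B to D | Composite | P(success) |
|---|---|---|---|
| 0% | 10% | 10.0% | 2.3% |
| 0% | 15% | 15.0% | 30.5% |
| 0% | 20% | 20.0% | 76.3% |
| 2% | 20% | 21.6% | 85.8% |
| 5% | 5% | 9.75% | 1.9% |
| 5% | 15% | 19.25% | 70.6% |
| 5% | 16.2% (B 2%, C 10%, D 5%) | 20.4% | 79.0% |
| 10% | 10% | 19.0% | 68.6% |

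For the seventh row: 1 − 0.98 × 0.90 × 0.95 = 0.162 for B to D, and 1 − 0.95 × 0.98 × 0.90 × 0.95 = 0.204 for the composite.

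**Step 4: what the data would then say about type A.** At a true type A rate of 5%, about 86 × 0.05 = 4.3 subjects would have such an event. An observed 4/86 has a 95% interval of 1.3% to 11.5%. Type A alone would reach 15/86 with probability 0.00002.

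The 76.3% in the third row is also the exact power at the design rate. The stated 80% comes from the normal approximation. That is a separate matter and does not affect this point.

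**The case against.** The best defence is that the formal plan is clear. The null, the alternative, the test, the alpha and the primary population are stated and agree across the documents, and the composite null follows directly after the loose sentence. That stands. No data item, analysis or error rate changes, and the composite test is valid.

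Three stronger readings are tempting, and the documents do not support them.

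- *A reader might infer that the plan commits the sponsor to announcing superior localization.* No passage says so. The protocol synopsis defines success as meeting the composite threshold, and the primary objective speaks more broadly of lesion visualization compared with standard techniques.
- *A reader might infer that Protocol 10.3.1 and 10.3.2 contradict each other*, because 10.3.1 says "The hypothesis to be tested is not a treatment comparison". That line follows a statement that this single-arm study has only one treatment, so it can be read as ruling out a comparison of arms. White light or palpation followed by NIR is a sequence within each subject.
- *A reader might infer that a lower bound for type A above 10% would justify the localization claim.* The documents set 10% for the composite only. Type A counts what NIR adds after standard techniques fail. It does not count lesions that standard techniques find and NIR misses, so even a high type A rate would show added yield and not superiority.

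It can also be said that the by-type summary will show type A. It will, and an interval could be computed from a count of subjects. But SAP 9.3 does not say whether its frequencies count subjects or events, and it gives no interval. SAP section 5, the exploratory material after SAP 3.2 and the table list are redacted, so the statement that nothing is planned for type A is limited to the visible text.

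**Conclusion.** The concern holds as a mismatch between the worded hypothesis and the tested quantity, in the current text of both documents. The Protocol (section 10) lets the SAP govern where the two differ, but that does not resolve it, because both carry the same sentence.

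It affects interpretation and claims, not the validity of the composite test. That rejection does not imply the worded hypothesis rests only on the endpoint definition and the 0/86 case. How likely such a result is cannot be known from the documents. The success probabilities of 71% to 79% quoted for low type A rates depend on assumed, independent component rates that put the composite near 20%. With B to D at 10% or less and type A at 5% or less, success is much less likely, as the table shows for two such cases.

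**What to change.** - In Protocol 10.3.2 and SAP 9.2, replace the primary hypothesis sentence with the claim under test: *more than 10% of subjects have one or more CSEs of any of types 1 to 4.* Remove the statement of superiority over white light and palpation for localizing known lesions.
- In SAP 9.3, add for each CSE type the number and proportion of subjects with at least one event of that type, with a two-sided 95% Clopper-Pearson interval, labelled descriptive.
- In SAP 9.3, state that rejecting H0 supports only the composite claim.
- Do not add a rule that permits a localization claim when the type A lower bound passes 10%.

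The cost is wording in two places, one more table and a narrower headline claim. Sample size, alpha and study conduct do not change. The change should be made before the SAP is finalized, which SAP section 1 places ahead of database lock.

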## 9.3. Analysis of the Primary Efficacy Endpoint

Efficacy analyses will be performed on the Evaluable population. This analysis will be repeated using the ITT population. Quantitative data will be presented as a standard set of summary statistics (n, mean, standard deviation, median, minimum, and maximum values). Categorical data will be expressed as frequency (%).

A one-sided exact binomial test will be used to test the null hypothesis using a one-sided alpha of .025, and Clopper-Pearson exact two-sided 95% confidence intervals will be reported. A right-sided p value will be provided, which is the probability of finding the observed number of successes (subjects with at least 1 CSE) or a larger number, given that the null hypothesis is true.

Frequency of CSEs will also be summarized by CSE type across subject characteristics including the following categories:

- Age
- Smoking history
- Overall cancer stage – pre-operative

- Overall cancer stage – post-operative
- Surgery type
- Primary lung cancer type
- Prior cancer treatment
- Imaging system
- Resection type
- Lesion type by histopathology

## 9.4. Secondary Efficacy Endpoints

### 9.4.1. Definition of Secondary Efficacy Endpoints

To evaluate the sensitivity, positive predictive value (PPV), and 1-PPV of VGT-309 with NIR imaging for lesion(s) *in vivo*:

4. Sensitivity is defined as the probability that the tissue fluoresces when it is cancer, as confirmed by histology  $(TP/(TP+FN))$  \*
5. Positive predictive value (PPV) is defined as the probability that a tissue sample contains cancer on histologic exam if it fluoresces  $((TP/(TP+FP))$  \*
6. One minus Positive predictive value (1-PPV) is defined as the probability that a tissue sample does not contain cancer when it fluoresces  $((FP/(TP+FP))$  \*

\* TP = true positive, FP = false positive, FN = false negative

### 9.4.2. Analysis Methods for Secondary Efficacy Endpoints

For the secondary endpoint analyses, sensitivity, PPV, and 1-PPV will be calculated and presented along with 95% confidence intervals for lesions and lymph nodes using *in vivo* assessments. Modeled point estimates and confidence intervals will be reported to account for the multiple dependent observations within subjects using Generalized Estimating Equations (GEE) since only between-subject observations can be modelled as independent. To account for the multiple dependent observations within a subject, the GEEs will be fit in SAS with an independent covariance matrix and binary (logit) outcomes. See Appendix 2.

Raw counts (%) will also be provided.

## 9.5. Exploratory Endpoints

### 9.5.1. Definition of Exploratory Endpoints

To evaluate the sensitivity, positive predictive value (PPV), and 1-PPV of VGT-309 with NIR imaging for lesion(s) *ex vivo*:

1. Sensitivity is defined as the probability that the tissue fluoresces when it is cancer, as confirmed by histology  $(TP/(TP+FN))$  \*
2. Positive predictive value (PPV) is defined as the probability that a tissue sample contains cancer on histologic exam if it fluoresces  $((TP/(TP+FP))$  \*

3. One minus Positive predictive value (1-PPV) is defined as the probability that a tissue sample does not contain cancer when it fluoresces  $((FP/(TP+FP))^*$

\* TP = true positive, FP = false positive, FN = false negative

## 10. SAFETY ANALYSES

### 10.1. Adverse Events and Deaths

Adverse events will be summarized by the Medical Dictionary for Regulatory Activities (MedDRA) system organ class and preferred term. Events will be summarized on the basis of the date of onset for the event. Only treatment-emergent adverse events (TEAEs), defined as any adverse event that begins on or after the date of administration of VGT-309, will be collected and analyzed in this study. For purposes of this document, AEs refers to TEAEs.

An overall summary of TEAEs will be provided. The following summaries (number and percentage of subjects) of TEAEs (by System Organ Class and Preferred Term) will be provided:

- TEAEs
- Treatment-related TEAEs
- TEAEs leading to study drug discontinuation
- Serious TEAEs
- Treatment-related Serious TEAEs

All AEs collected during the study will be presented in a listing. Additionally, a listing will be provided for any AEs leading to death.

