9.2.1 Adverse Events

NOTE: The content of this section is based on the FDA “Guidance for Industry and Investigators; Safety Reporting Requirements for IND and BA/BE Studies” issued in December 2012. A copy of this guidance will be provided in the to the site upon request and should be referred to if and when the following do not provide sufficient guidance for an investigator to make an assessment regarding the occurrence, severity, relationship and expectedness of an adverse event (AE).

Adverse event solicitation and recording will begin immediately upon start of dosing with the study product (VGT-309) and will include only on-treatment (treatment-emergent) events. Any changes to a subject’s health that occur between the signing of the informed consent and start of dosing will be recorded as updates to the subject’s medical history.

Subjects will be instructed to report AEs during the study and staff will query subjects regarding AEs throughout the study. The Investigator (and/or designee) must document all AEs reported from the time of dosing through completion of the End-of-study Visit (Days 25 -35). Any subject who is withdrawn from the study due to an AE shall be followed until the event has resolved or stabilized or 30 days after last dose and the Investigator will document available follow-up information on the subject’s source documentation and CRF.

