9.2.1.2 Evaluating and Reporting of Adverse Events

All AEs (i.e., a new event or an exacerbation of a pre-existing condition) that occur after the start of dosing with VGT-309 and through the end of the study - as evaluated in the End-of-Study Visit (Days 25 – 35) - or, if the subject is withdrawn due to an AE, must be recorded as an AE or SAE (if applicable), on the Adverse Event eCRF. The Investigator must follow all AEs until the AE resolves, or until the Investigator and/or the Medical Monitor determine the event is chronic or clinically stable. If an AE remains unresolved at the conclusion of the study, the Investigator and Medical Monitor will make a clinical assessment to determine whether continued follow-up of the AE is warranted. All subjects who have received any exposure to VGT-309 (even if dosing is not completed) must be evaluated for AEs.

The Investigator should attempt to establish a diagnosis of the event based on signs, symptoms and/or other clinical information. In such cases, the diagnosis should be documented as the AE and not the individual signs/symptoms.

All AEs or SAEs must be promptly documented on the Adverse Event eCRF and assessed by the Investigator. Details of the event must include the dates of onset and resolution, severity, relationship to study drug, seriousness, and whether the event caused the subject to withdraw from the study, outcome and timing with regard to administration of the study drug.

Grade: Each AE will be assigned a “Grade” based on the Common Terminology Criteria for Adverse Events (CTCAE). Version 5.0 of the CTCAE will be used for this study. Refer to Section 9.1.2 for stopping rules based on the assigned Grade of AE.

Severity: Severity should be graded and recorded as follows:

- Mild: Awareness of event but easily tolerated.
- Moderate: Discomfort enough to cause interference with usual activity.
- Severe: Inability to carry out usual activity, incapacitating, requires medical intervention.

Relationship: The relationship of the Adverse Event to the study drug will be determined by the Principal Investigator, and assessed using the following definitions:

- **Related:** There is a distinct temporal relationship between the event onset and administration of the study drug. There is a known reaction to agent or chemical group or predicted by known pharmacology. The event cannot be explained by subject’s clinical state or other factors.

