10.4.1 Adverse Events

No statistical testing will be performed for safety data.

Adverse events will be summarized by the Medical Dictionary for Regulatory Activities (MedDRA) system organ class and preferred term. The MedDRA version current at the start of the study will be used throughout the study. A treatment-emergent adverse event (TEAE) is defined as any adverse event that begins on or after the date of administration of VGT-309.

An overall summary of TEAEs will be provided. The following summaries (number and percentage of subjects) of TEAEs (by System Organ Class and Preferred Term) will be provided:

- TEAEs.
- Treatment-related TEAEs.
- TEAEs leading to study drug discontinuation (infusion interruption or discontinuation)
- Serious TEAEs.
- Treatment-related Serious TEAEs.

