## 4. STUDY DESIGN

This is a Phase 2, multi-center, open-label study to evaluate the safety and efficacy of VGT-309, a tumor-targeted, activatable fluorescent imaging agent, in subjects undergoing surgery for proven or suspected cancer in the lung. Approximately 100 subjects will be enrolled to ensure at least 86 subjects are evaluable with the option to expand enrollment by protocol amendment if deemed necessary by the DSC (Data Safety Committee) to meet primary and/or secondary objectives.

Following agreement with and signing of the informed consent, subjects will undergo screening measurements for the study within 4 weeks prior to the anticipated dosing:

1. Medical, surgical and medication history.
2. Complete physical exam, including vital signs and height
3. Weight (needed for dose calculation)
4. Chemistry, hematology, coagulation and urinalysis with microscopy clinical laboratory studies.
5. 12-lead ECG.
6. Serum pregnancy test for females of child-bearing potential.

After meeting all enrollment criteria, each subject will receive 0.32 mg/kg VGT-309 by IV administration 12-36 hours prior to the induction of general anesthesia for surgery (refer to section 4 of protocol v3.0). Subjects will be observed for 1 hour after dosing is completed and asked about possible treatment emergent adverse events.

Subjects will undergo surgical resection within 12-36 hours after completion of VGT-309 dosing. Measurements of efficacy will be taken during surgery and during the pathological examination of all surgical specimens.

Following surgery, subjects will be monitored for safety during their hospitalization. Between 7 to 14 and 25 to 35 days after surgery, the subjects will return to the clinic or have a telehealth visit for final safety assessments. At the last visit, if there are no adverse events requiring further follow up, subjects will then be released from the study.

If a subject chooses to withdraw from the study prior to the final visit, they will be asked to undergo a final safety assessment before their departure.

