#### **10.1.5. Summaries of Adverse Events and Deaths**

Summaries (number and percent of subjects) of adverse events (by SOC, and PT) will be provided using the safety analysis set as follows:

- All treatment-emergent adverse events,
- All treatment-emergent treatment-related adverse events,

- All treatment-emergent treatment-related serious adverse events,
- All treatment-emergent adverse events that caused permanent discontinuation from study drug,
- All treatment-emergent adverse events leading to death.

A brief overall summary of TEAEs will show the number and percentage of subjects who had at least one of each of the above categories.

Multiple events will be counted once only per subject in each summary. For data presentation, SOC will be ordered alphabetically, with PT sorted by decreasing total frequency. For summaries by severity grade, the most severe event will be selected. In addition to the presentation by SOC, each summary will also be presented by preferred term only, ordered by decreasing frequency.

In addition to the summaries, data listings will be provided for the following:

- All treatment-related adverse events
- Serious adverse events
- Deaths
- Adverse events leading to discontinuation of study drug

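### The readable TEAE summaries do not separate the 12-36 hours before surgery from the weeks after it, so drug-related events are obscured for terms that are also common after surgery

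*SAP*

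**What the plan says.** **Definition.** SAP 10.1 states: "Only treatment-emergent adverse events (TEAEs), defined as any adverse event that begins on or after the date of administration of VGT-309, will be collected". Protocol 10.4.1 has the same rule, and protocol 9.2.1 carries collection through the end-of-study visit on Days 25-35.

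**Placement and counting.** SAP 10.1: "Events will be summarized on the basis of the date of onset for the event". SAP 10.1.5: "Multiple events will be counted once only per subject in each summary". The readable summaries by system organ class and preferred term cover all, related, serious, related serious, discontinuation and fatal TEAEs. None is divided at surgery.

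**Sequence of events.** SAP 4: "Subjects will undergo surgical resection within 12-36 hours after completion of VGT-309 dosing". Safety visits follow "Between 7 to 14 and 25 to 35 days after surgery". Protocol 6.1.4 puts surgery on Day 1 or 2, protocol 9.2.2 counts complications in hospital as AEs, and protocol 10.3.1 confirms a single unblinded arm.

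**Timing data.** For each AE, protocol 9.2.1.2 asks for onset and resolution dates and for "outcome and timing with regard to administration of the study drug".

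**The concern.** The safety objective concerns VGT-309, not the operation. Between the start of dosing and induction of anesthesia, an AE cannot be a complication of the operation. A rate for that interval is the nearest thing to a drug-specific AE rate that this single-arm design can give, and no readable text plans one.

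The counting rule adds to the problem. A subject with nausea after the infusion and again after surgery is one count, the same as a subject with post-operative nausea only. For terms common after thoracic surgery, the pooled percentage then says little about the drug, and the reader has no comparator to subtract.

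**Working it through.** The documents give no AE rate, safety precision or safety sample size, so there is no planned figure to reproduce.

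**1. Share of observation time before surgery.** Inputs: 12-36 hours from dose to surgery (0.5 to 1.5 days) and a last visit 25-35 days after surgery (SAP 4). Share = pre-surgery days / (pre-surgery days + follow-up days).
- Smallest: 0.5 / (0.5 + 35) = 1.4%.
- Largest: 1.5 / (1.5 + 25) = 5.7%.

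**2. What pooling does to a drug effect.** Assumptions: about 100 subjects (SAP 4), a drug-caused rate *d* before induction, a surgical background *b* for the same term, and independence. With each subject counted once, the pooled rate is 1 - (1 - *b*)(1 - *d*).

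For *b* = 30% and *d* = 5%: 1 - 0.70 × 0.95 = 33.5%. The increment is 3.5 points, not 5, because 0.30 × 0.05 = 1.5% of subjects have both events and count once.

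Expected counts rounded to whole subjects, with exact (Clopper-Pearson) 95% CIs:

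| *d* | *b* | Pooled rate | Count | 95% CI | Contains *b*? |
|---|---|---|---|---|---|
| 3% | 30% | 32.1% | 32/100 | 23.0%-42.1% | yes |
| 5% | 20% | 24.0% | 24/100 | 16.0%-33.6% | yes |
| 5% | 30% | 33.5% | 34/100 | 24.8%-44.2% | yes |
| 10% | 20% | 28.0% | 28/100 | 19.5%-37.9% | yes, narrowly |
| 10% | 10% | 19.0% | 19/100 | 11.8%-28.1% | no |

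Over all combinations of *d* = 3%, 5%, 10% with *b* = 10%, 20%, 30%, 50%, the pooled interval contains the background in every case except the last row.

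**3. The same effects in a pre-induction column**, assuming almost no background there: 3/100 gives 0.6%-8.5%, 5/100 gives 1.6%-11.3%, and 10/100 gives 4.9%-17.6%. Zero events would give an upper bound of 3.6%.

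**4. What else covers the pre-surgery interval.** Protocol 6.1.3 schedules triplicate ECGs at 1-10 and about 30 minutes after the dose and vital signs at 30 and 60 minutes. Subjects may leave after 1 hour. In the readable visit text, the next vital signs and the first routine post-dose laboratory tests are at the in-hospital visit on Day 3 +/- 1 (protocol 6.1.5). From about 1 hour after the dose until induction, AE reports are therefore the only safety data described.

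**The case against.** A reader might infer that the plan hides drug effects altogether, or that the unblinded investigator's related/unrelated call is the only thing left to separate drug from surgery. The documents do not support either reading.
- ECGs and vital signs are summarised by time point against baseline (SAP 10.3, 10.5). An acute change in blood pressure after infusion would show there without any attribution.
- Protocol 10.4.1 tabulates TEAEs that interrupt or stop the infusion. With a single infusion of 15-20 minutes, these arise before surgery. (SAP 10.1.5 names only permanent discontinuation.)
- All AEs are listed, with onset dates collected, and related and related-serious tables are planned. SAP 10.1.3 counts a missing relationship as related.
- The Data Safety Committee evaluates related SAEs and attributed AEs above Grade 2 (protocol 9.1.2.1).

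These safeguards stand, with limits. The definition of related in SAP 10.1.3 includes that clinical state or other factors cannot explain the event, which pushes overlapping post-operative terms towards unrelated. Listings give no rates by term.

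Three further objections also stand. The list of tables in SAP Appendix 1 is redacted, so a by-period table cannot be ruled out, and the appendix allows tables to be split without an SAP amendment. The rates in the illustration are assumed, and protocol 10.4.1 plans no safety tests, so the intervals show how readable the tables are and are not a planned inference. The sentence on onset date is not itself an error; the gap is the missing period split combined with the TEAE definition and the counting rule.

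**Conclusion.** The point holds as a cheap improvement to reporting. On the readable text, the all-TEAE and serious-TEAE tables combine a pre-surgery interval of 1.4% to 5.7% of observation time with 25-35 post-operative days, and so will mostly describe thoracic surgery. For terms common after surgery, drug-related events are obscured, though not hidden. What is not tabulated separately is the set of AE reports from about 1 hour after the dose until induction.

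The time shares follow from the documents. The size of the masking does not: it rests on assumed drug rates of 3%-10%, assumed backgrounds of 10%-50%, independence and 100 subjects. The conclusion is also conditional on the redacted table list not already containing a split. The primary endpoint is not affected, and the documents do not contradict themselves on this counting.

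**What to change.** In SAP 10.1 and 10.1.5, keep the total column and add columns by onset period, counting each subject once per term within each period:
- (a) start of dosing to induction of anesthesia;
- (b) induction to end of study;
- day of surgery, timing unknown: events with onset on the surgery date that cannot be placed before or after induction from the onset date and the recorded timing relative to dosing.

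Add a sensitivity count that moves the third group into (a). Assigning those events to (a) by default would put possible operative events into the column meant to exclude the operation. Keeping them apart also covers surgery on either Day 1 or Day 2.

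The documents tie the 12-36 hour window sometimes to induction and sometimes to surgery or resection (protocol 3 and 4.4; SAP 4), and these passages must be reconciled. Using induction as the table boundary is an analysis definition only and takes no position on the dosing window.

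**Cost.** SAP wording and programming, with no new visits. The readable text does not confirm that clock time of onset is collected; if it is not, the third column will be larger. Period (a) is short and unevenly observed, since subjects may leave after 1 hour. It excludes the operation but not underlying disease or concomitant medication. Routine post-dose laboratory findings will still fall in (b).
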